### **ANNEX 3 – SCINTIGRAPHY EXTERNAL REVIEW**

In this study, all the scintigraphy tests will be additionally reviewed by two external evaluators.

The objective of this evaluation will be to assess the level of discrepancy in the evaluation of the scintigraphy or SPECT images by different evaluators

All the scintigraphy tests will be uploaded in a dedicated database via the study web site.

Two experts from the scientific committee members will connect to the study web site with personalized connection access. They'll review the scintigraphies and enter their grading evaluation.

**ABBREVIATIONS**

Abbreviation	Definition
 mTc-DPD	99mTechnetium-3,3-diphosphono-1,2-propanodi-carboxylic acid
 mTc-PYP	99mTechnetium-pyrophosphate
 mTc-HMDP	99mTechnetium-hydroxymethylene diphosphonate
AA	Serum Amyloid A Protein
AE	Adverse event
AICD	Automatic Implantable Cardiac Defibrillator
AL	Light chain amyloidosis
ATTR	Transthyretin amyloidosis
ATTR-CM	Transthyretin amyloid cardiomyopathy
ATTRv	Variant transthyretin related amyloidosis
ATTRwt	Wild type transthyretin related amyloidosis
AVA	Aortic valve area
CI	Confidence interval
CM	Cardiomyopathy
CTS	Carpal Tunnel syndrome
ECG	Electrocardiogram
ECHO	Echocardiography
e-CRF	Electronic Case Report Form
FAS	Full analysis set
HCM	Hypertrophic cardiomyopathy
IQR	Interquartile Range
LGE	Late gadolinium enhancement
LV	Left ventricular
LVH	Left ventricular hypertrophy
LVOTO	Left ventricular outflow tract obstruction
MRI	Magnetic resonance imaging
MWT	Maximal wall thickness
NI	Non-interventional
NT-proBNP	N-terminal pro-brain natriuretic peptide
PN	Polyneuropathy
PT	Preferred term
SAE	Serious adverse event
SAF	Safety analysis set
SCD	Sudden cardiac death
sFLC	Serum Free Light Chain
SOC	System Organ Class
SPECT	Single Photon Emission Computed Tomography
TTR	Transthyretin

PFIZER CONFIDENTIAL

## 1 AMENDMENTS FROM PREVIOUS VERSION(S)

Version	Effective Date	Change Type (New, Revise, Admin)	Summary of Revisions
1	27-Apr-2020	New	
2	06-Jul-2022	Revise	
 
• Wording modified in line with clarifications in protocol amendment 2
 
• To add sensitivity analyses to assess the impact of:               
 
○ using a SPECT
 
○ no longer using a centralized lab
 
 
 
• Subgroups analyses added
 
• To add scintigraphy discrepancies analysis
 

## 2 INTRODUCTION

Note: in this document any text taken directly from the non-interventional (NI) study protocol is *italicised*.

*The main purpose of this study is to determine the prevalence of transthyretin amyloid cardiomyopathy (ATTR-CM) among patients admitted due to left ventricular hypertrophy (LVH) of unknown etiology when radionuclide bone scintigraphy or single photon emission computed tomography (SPECT) is used.*

[figure not shown]

Figure 1. Diagnostic algorithm for patients with suspected amyloid cardiomyopathy (Gillmore 2016).

## 2.1 STUDY DESIGN

*TTRACK* is an epidemiological multicenter and multinational study.

### Study population

This study will include *patients with LVH from undiagnosed etiology and the following inclusion/exclusion criteria:*

#### 1. Inclusion criteria:

- a. Patient signed inform consent.
- b. Males and Females.
- c. Age  $\geq 50$  years.
- d. Left ventricular hypertrophy (LVH) defined as end-diastolic LV maximum wall thickness (MWT)  $\geq 15$ mm in Echocardiogram.

- e. *Plan to undergo or recently underwent radionuclide bone scintigraphy and/or SPECT with any of the following radio labelled tracers:  $^{99m}\text{Tc}$ -DPD or  $^{99m}\text{Tc}$ -PYP or  $^{99m}\text{Tc}$ -HMDP.*

*Scintigraphy will be defined at each site according to the standard grading:*

*Grade 0 = absent cardiac uptake*

*Grade 1 = mild uptake less than bone*

*Grade 2 = moderate uptake equal to bone*

*Grade 3 = high uptake greater than bone*

## 2. Exclusion criteria

- a. *Etiological diagnosis explaining the LVH prior to patient inclusion (eg, Sarcomeric HCM, Myeloma, Fabry disease, Sarcoidosis, any type of amyloidosis [AA, AL, TTR\*\*])*

*\*\* TTR diagnosis at exclusion criteria: Direct relative (siblings or parents) of a carrier with a known hereditary mutation in the TTR gene or any patient already diagnosed by any of the following: cardiac fixation at the bone scintigraphy, TR mutation at the genetic testing, biopsy with amyloidosis (positive red congo) and positive TTR staining.*

- b. *Severe aortic stenosis defined as aortic valve area (AVA) < 1.0 cm^2*

### Data source

*Data will come from medical records and will be collected in routine clinical practice. As an epidemiological study, there are no specific requirements with regard to patient procedures to be performed or the treatment regimen. Data from each patient will be reported on an electronic case report form (e-CRF).*

### Treatment/cohort labels

NA

## 2.2 STUDY OBJECTIVES

### 1. Primary objective

- To assess the prevalence of patients with cardiac fixation at the radionuclide bone scintigraphy and/or Single Photon Emission Computed Tomography (SPECT) performed with  $^{99m}\text{Tc}$ -DPD or  $^{99m}\text{Tc}$ -PYP or  $^{99m}\text{Tc}$ -HMDP\* among patients with (left ventricular hypertrophy) LVH from undiagnosed etiology;*

### 2. Secondary objectives

- *To assess the prevalence of Light Chain Amyloidosis (AL) or Transthyretin amyloid (ATTR) amyloidosis in patients with cardiac fixation at the bone scintigraphy (visual grade 1 to 3) and/or SPECT;*
- *To assess the prevalence of hereditary (ATTRv) and wild-type (ATTRwt) ATTR amyloidosis in patients diagnosed with ATTR amyloidosis;*
- *To describe TTR genetic mutations\*\* in patients with ATTRv amyloidosis;*
- *To assess the prevalence of patients with familial history of known cardiomyopathy (CM), polyneuropathy (PN), sudden cardiac death (SCD) among their relatives (ie, parents, siblings and 2nd/3rd degree grade family members);*
- *To assess the prevalence in patients with cardiac fixation at the bone scintigraphy or SPECT of concomitant signs or symptoms of ATTR amyloidosis, ie,:*
  - *Sensori-motor Polyneuropathy (PN);*
  - *Carpal Tunnel syndrome (CTS);*
  - *Autonomic dysfunction;*
  - *Cardiological manifestations;*
  - *Laboratory signs;*
- *To compare the clinical and biochemical characteristics between patients with positive scintigraphy (cardiac fixation at the bone scintigraphy grade 1, 2 or 3) and/or SPECT;*
- *To assess the level of discrepancy in the evaluation of the scintigraphy and/or SPECT images by different evaluators.*

\* *Bisphosphonate (99mTc-DPD/99mTc-PYP/99mTc-HMDP) Scintigraphy*

\*\* *Variant and pathogenic mutation by sequencing the coding parts*

### **3 INTERIM ANALYSES**

*An interim analysis of the data collected was planned for all the variables as soon as 75 patients will be selected with a scintigraphy grade 1, 2 or 3 and with completed e-CRF. This interim analysis was finally not performed.*

In addition, an interim analysis was performed for publication purpose, all patients screened until the May 11th 2020 were included in this analysis. Considering the expected number of patients with a scintigraphy grade 1, 2 or 3, all analyses described in this SAP were done, except multivariate analyses planned in 0.

## **4 HYPOTHESES AND DECISION RULES**

### **4.1 STATISTICAL HYPOTHESES**

TTRACK is a non-interventional and uncontrolled study. In that sense, there is no inferential hypothesis that will serve for a claim.

## 4.2 STATISTICAL DECISION RULES

The analysis of this study will be mainly descriptive. However, factors associated to ATTR will be identified using a multivariate analysis. All statistical tests will be exploratory in nature.

## 5 ANALYSIS SETS/POPULATIONS

### 5.1 FULL ANALYSIS SET

#### **Full Analysis Set 1 – Primary population**

Full Analysis Set 1 (FAS1) includes all patients who meet eligibility (inclusion/exclusion) criteria and with a radionuclide bone scintigraphy and/or SPECT performed with 99mTc-DPD/99mTc-PYP/99mTc-HMDP.

#### **Full Analysis Set 2 – All FAS1 patients with positive scintigraphy (grade 1, 2 or 3)**

Full Analysis Set 2 (FAS2) is a subset of FAS1 patients with grading of cardiac retention equal to grade 1, grade 2 or grade 3.

Analysis of group 1 vs group 2&3 independently and grouped will be performed. Patients with grade 1 will be considered as “undetermined etiology”

#### **Full Analysis Set 3 – All FAS2 patients with positive scintigraphy grade 2 or 3 (Cardiac amyloidosis)**

Full Analysis Set 3 (FAS3) is a subset of FAS2 patients with grading of cardiac retention equal to grade 2 or grade 3.

**FAS 3.1** Patients with grade 2-3 **without** monoclonal protein abnormalities (ATTR amyloidosis)

**FAS 3.2** Patients with grade 2-3 **with** monoclonal protein abnormalities (Undefined etiology, cardiac ATTR amyloidosis, or MGUS or AL Amyloidosis). Monoclonal protein abnormalities if defined as Positive IFE (serum and/or urine) or positive FLC (See definition in section 6.3).

### 5.2 SAFETY ANALYSIS SET

Safety Analysis Set (SAF) includes all enrolled patients.

### 5.3 SUBGROUPS

Some secondary endpoints (See table in section 8.2) will also be described by the following subgroup:

- ATTRv: ATTR patients with a ATTR gene sequencing with variant transthyretin will be considered as ATTRv.

- ATTRwt: ATTR patients with a ATTR gene sequencing with a result of « No Mutation » will be considered as ATTRwt

## 6 ENDPOINTS AND COVARIATES

### 6.1 EFFICACY/EFFECTIVENESS ENDPOINTS

NA

### 6.2 SAFETY ENDPOINTS

Adverse events (AE) will be coded using MedDRA version 20.0 or later.

### 6.3 OTHER ENDPOINTS

#### Primary endpoint

Patients with cardiac fixation at the radionuclide bone scintigraphy and/or SPECT performed with 99mTc-DPD or 99mTc-PYP or 99mTc-HMDP will be defined as patients with a cardiac retention of grade 1, grade 2 or grade 3.

Patients without cardiac fixation at the radionuclide bone scintigraphy performed and/or SPECT with 99mTc-DPD or 99mTc-PYP or 99mTc-HMDP will be defined as patients with a cardiac retention of grade 0.

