## **8 STATISTICAL METHODOLOGY AND STATISTICAL ANALYSES**

### **8.1 STATISTICAL METHODS**

Quantitative variables will be described using number of filled and missing data, mean, standard deviation, median, 1st and 3rd quartiles, minimum and maximum. The 95%CI of the mean will also be provided, assuming a normal distribution. In case of departure from normality, results will be interpreted based on median and Interquartile Range (IQR).

Qualitative variables will be described using number of filled and missing data and, for each modality, the frequency and percentage (referring to filled data). A 95% confidence interval (CI) will be associated to binomial proportions using the Wilson score method.

Factors associated to an outcome of interest (ATTR vs other and ATTRwt vs ATTRv within patients diagnosed with ATTR-CM) will be identified using univariate logistic regression models. A separate logistic regression model will be created for each factor (as well as covariates described in section 6.4). If the variable is significantly associated to the outcome at the 10% level then the factor will be put forward into a multivariate model. Once the univariate model selection is complete, backwards selection will be used to remove factors from the multivariate model which do not have a significant p value at the 5% level. The covariate with the highest p value will be removed in turn until all factors have a p value less than 0.05. If a significant interaction is found then the individual factors of this interaction will be kept in the model, regardless of their p value. A significant interaction is tested for between all variables in the multivariate model.

Furthermore, a table showing all of the 95% confidence intervals and p values for the odds ratios coming from the univariate and multivariate models will be created.

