### Analysis of primary and secondary objectives

For each objective, a percentage/prevalence with its 95%CI will be assessed overall and in the sub-groups defined in section 5.3 if pertinent.

Endpoints	Population or Subgroup
Percentage of patients with cardiac fixation at the radionuclide bone scintigraphy and/or SPECT performed with 99m Tc-DPD or 99m Tc-PYP or 99m Tc-HMDP among patients with (left ventricular hypertrophy) LVH from an undiagnosed etiology	FAS1
Prevalence of Transthyretin amyloid (ATTR) or patients with suspicion of MGUS / AL amyloidosis	FAS1
Prevalence of hereditary (ATTRv) and wild-type (ATTRwt) ATTR amyloidosis in patients with positive scintigraphy	FAS2 & 3 (including 3.1 and 3.2)
Prevalence of TTR genetic mutation in patients with positive scintigraphy	FAS2 & 3 (including 3.1 and 3.2)
Prevalence of patients with familial history of known cardiomyopathy (CM), polyneuropathy (PN), sudden cardiac death (SCD) among their relatives (parents, siblings and 2 nd /3 rd grade family)	FAS1, 2 & 3 (including 3.1, 3.1(ATTRv), 3.1(ATTRwt) and 3.2)
Prevalence of patients with Senso-motor Polyneuropathy	FAS2 & 3 (including 3.1, 3.1(ATTRv), 3.1(ATTRwt) and 3.2)

PFIZER CONFIDENTIAL

Endpoints	Population or Subgroup
Prevalence of patients with CTS	FAS2 & 3 (including 3.1, 3.1(ATTRv), 3.1(ATTRwt) and 3.2)
Prevalence of patients with autonomic dysfunction	FAS2 & 3 (including 3.1, 3.1(ATTRv), 3.1(ATTRwt) and 3.2)
Prevalence of patients with cardiological manifestations	FAS2 & 3 (including 3.1, 3.1(ATTRv), 3.1(ATTRwt) and 3.2)
Prevalence of patients with laboratory signs	FAS2 & 3 (including 3.1, 3.1(ATTRv), 3.1(ATTRwt) and 3.2)
Description of the clinical and biochemical characteristics between patients with positive scintigraphy (cardiac fixation at the bone scintigraphy grade 1, 2 or 3) and/or SPECT (See section 0 § 3).	FAS2 & 3 (including 3.1, 3.1(ATTRv), 3.1(ATTRwt) and 3.2)
Discrepancy in the evaluation of the scintigraphy and/or SPECT images by different evaluators (See section 0 § 7)	FAS1

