**Table 15.1.1 Number and Percentage of Patients in Each Analysis Set**

Analysis Set		Grade 0 (N=XX)	Grade 1 (N=XX)	Grade 2 (N=XX)	Grade 3 (N=XX)	Unknown grade (N=XX)	Total (N=XX)
Selected	No						xx (xx.x%)
	Yes						xx (xx.x%)
FAS1	No	xx (xx.x%)	xx (xx.x%)	xx (xx.x%)	xx (xx.x%)	xx (xx.x%)	xx (xx.x%)
	Yes	xx (xx.x%)	xx (xx.x%)	xx (xx.x%)	xx (xx.x%)	xx (xx.x%)	xx (xx.x%)
FAS2	No		xx (xx.x%)	xx (xx.x%)	xx (xx.x%)	xx (xx.x%)	xx (xx.x%)
	Yes		xx (xx.x%)	xx (xx.x%)	xx (xx.x%)	xx (xx.x%)	xx (xx.x%)
FAS3	No		xx (xx.x%)	xx (xx.x%)	xx (xx.x%)	xx (xx.x%)	xx (xx.x%)
	Yes		xx (xx.x%)	xx (xx.x%)	xx (xx.x%)	xx (xx.x%)	xx (xx.x%)
FAS4	No		xx (xx.x%)	xx (xx.x%)	xx (xx.x%)	xx (xx.x%)	xx (xx.x%)
	Yes		xx (xx.x%)	xx (xx.x%)	xx (xx.x%)	xx (xx.x%)	xx (xx.x%)
Safety Set	No	xx (xx.x%)	xx (xx.x%)	xx (xx.x%)	xx (xx.x%)	xx (xx.x%)	xx (xx.x%)
	Yes	xx (xx.x%)	xx (xx.x%)	xx (xx.x%)	xx (xx.x%)	xx (xx.x%)	xx (xx.x%)

...

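### SAP 6.3 and FAS2 classify patients by a 0–3 grade without saying whether it includes the SPECT result that the objectives count, so discordant and SPECT-only patients have no clear primary endpoint status

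*SAP*

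**What the plan says.** The primary objective in SAP 2.2 is "To assess the prevalence of patients with cardiac fixation at the radionuclide bone scintigraphy and/or Single Photon Emission Computed Tomography (SPECT") among patients with unexplained LVH. The secondary objective on AL and ATTR is set "in patients with cardiac fixation at the bone scintigraphy (visual grade 1 to 3) and/or SPECT". Protocol section 8 has the same scope. Protocol 9.4 uses an explicit either/or rule: the post-imaging visit is documented if the scintigraphy is grade 1 to 3 or the SPECT shows fixation. The follow-up visit (9.2.5.1) and the additional CRF variables (Abstract, Variables) are triggered in the same way. Protocol 9.3 lists the 0–3 grade under scintigraphy, and a SPECT date and SPECT result under a separate SPECT source.

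FAS1 admits eligible patients "with a radionuclide bone scintigraphy and/or SPECT performed with" one of the three tracers, so SPECT alone is enough. In SAP 6.3, patients with fixation on scintigraphy and/or SPECT "will be defined as patients with a cardiac retention of grade 1, grade 2 or grade 3", and patients without fixation are those with grade 0. FAS2 "is a subset of FAS1 patients with grading of cardiac retention equal to grade 1, grade 2 or grade 3". In the SAP 8.2 endpoint table, the row on clinical and biochemical characteristics covers "positive scintigraphy (cardiac fixation at the bone scintigraphy grade 1, 2 or 3) and/or SPECT", with FAS2 and FAS3 as its populations. Table shell 15.1.1 has a column headed "Unknown grade".

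The SAP 8.2 sensitivity analysis on the use of SPECT reports the primary prevalence separately for patients included before and after Amendment 2 (11 February 2020).

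**The concern.** The objective has two routes to a positive result, while the endpoint rule has one scale. Nothing in the SAP maps a SPECT result to that scale or says which result prevails when the two modalities disagree. Two groups are therefore unsettled: patients with planar grade 0 and fixation on SPECT, and patients who had SPECT only and carry no grade.

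What is at stake is the primary estimate and membership of FAS2. A grade-0, SPECT-positive patient qualifies for follow-up and for laboratory and genotyping data collection because of the SPECT, yet may be counted negative and be absent from every FAS2 table. The sensitivity analysis labelled as addressing SPECT applies the same endpoint in two calendar periods. It mixes any SPECT effect with other changes over time or from Amendment 2, and it never compares the two definitions in the same patients.

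**Working it through.** **1. The two readings.**

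- *Reading A: the grade is the scintigraphy grade.* Protocol 9.3 keeps the SPECT result apart from the grade, and protocol 9.4 adds SPECT as an alternative to grades 1–3. The heading of FAS2 refers to positive scintigraphy, and the ATTR/AL endpoint in SAP 6.3 refers to grades at scintigraphy. On this reading, grade 0 with SPECT fixation is negative and outside FAS2, and an ungraded SPECT-only patient is in FAS1 with neither status.
- *Reading B: SPECT images are graded too.* Protocol 9.2.2 introduces the 0–3 grading after naming both modalities, and the agreement grid in SAP 8.2 (Other analyses, item 7) covers scintigraphy or SPECT images. On this reading, a patient graded 0 on planar and 1 or more on SPECT satisfies both definitions in SAP 6.3, with no precedence rule.

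Neither reading gives a complete rule.

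**2. The plan's own precision.** Inputs: prevalence p = 10% and N = 1500 (protocol 9.5), and a 95% two-sided interval.

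Half-width = 1.96 × √(0.10 × 0.90 / 1500) = 1.52 points, which matches the stated 1.5. The Wilson interval (SAP 8.1) for 150/1500 is 8.58% to 11.62%. At the 1000 patients named as a minimum in the protocol's amendment table, the half-width is 1.86 points.

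**3. Grade 0 with SPECT fixation (Reading A, or Reading B if the planar grade prevails).** Let d be the share of FAS1 in this group. The documents do not give d, so the values below are assumptions. If the true any-modality prevalence is p, the grade rule estimates p − d, an error of −d. The share of true positives missing from FAS2 is d/p. Coverage is the probability, with the count distributed Binomial(N, p − d), that the 95% Wilson interval contains p = 10%.

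| d (assumed) | Patients of 1500 | Error (points) | Missing from FAS2 | Coverage, N=1500 | Coverage, N=1000 |
|---|---|---|---|---|---|
| 0 | 0 | 0 | 0 | 94.7% | 94.9% |
| 0.25% | 3.75 | −0.25 | 2.5% | 93.8% | 94.4% |
| 0.5% | 7.5 | −0.5 | 5% | 90.3% | 92.3% |
| 1% | 15 | −1.0 | 10% | 74.8% | 82.5% |

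The error equals the planned half-width when d is about 1.5% (0.0152 × 1500 ≈ 23 patients).

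**4. SPECT-only patients without a grade (Reading A).** Let s be their share of FAS1 and q their positivity; both are assumed. SAP 8.1 reports "the frequency and percentage (referring to filled data"), and SAP 7 imputes nothing, so these patients would leave the denominator. With 10% positive among graded patients, the objective's prevalence is (1 − s) × 10% + s × q and the reported value is 10%. The error is −s × (q − 10%). For s = 5%:

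- q = 5%: +0.25 points
- q = 10%: 0
- q = 20%: −0.5 points

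If they were instead kept in the denominator as not positive, the reported value would be 0.95 × 10% = 9.5%. The SAP does not say explicitly which treatment applies to them.

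**The case against.** The strongest reply is that SAP 6.3 already covers SPECT. The sentence defining fixation names both modalities and speaks of cardiac retention, not of a planar grade. With protocol 9.2.2 and the agreement grid, the authors may have meant every scan to be graded 0–3, and then the characteristics row in SAP 8.2 is consistent with FAS2. The coding of the SPECT result is in the e-CRF, which is not among the documents. This stands as far as it goes: a reader might infer that the plan demonstrably drops SPECT-positive patients and underestimates the primary prevalence, and the documents do not support that. They leave the rule open, and Reading B still fails on discordant grades.

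A reader might also infer that such patients would go unseen. That is too strong. SAP 8.2 (Other analyses, item 3) describes all CRF variables by grade in FAS1, which should include the SPECT result among grade-0 patients, and shell 15.1.1 shows ungraded patients. These displays would partly reveal the cases, but they would not classify them or give the prevalence under the other definition.

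On size, the DPD method in Annex 2 acquires SPECT in patients who already show uptake, so discordant cases may be few. That also stands. They are not ruled out: Annex 2 describes one of three permitted tracers, imaging is routine care, and eligibility allows SPECT alone.

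Finally, a before/after split is a fair way to describe an amendment's impact, and the study is mainly descriptive. The split is worth keeping; it does not answer what SPECT adds.

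**Conclusion.** The mismatch is real and concerns definition, not sample size. The objectives and protocol 9.4 count fixation on either modality. SAP 6.3 and FAS2 use a grade whose relation to the SPECT result is not stated, and no rule covers discordant or ungraded patients. The text leans towards the scintigraphy grade but does not settle it.

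The size is unknown. Wherever a grade-0, SPECT-positive patient is counted negative, the error is downward, at 1 point per 1% of FAS1. For ungraded SPECT-only patients it can go either way. The coverage figures rest on assumed shares and should not be read as expected performance: at 0.25% the loss is slight (93.8% against 94.7% at N=1500), and Annex 2 makes the low end plausible. They also borrow the planning value of 10%, which protocol 9.5 states for ATTR-CM, not for any fixation. The point should be fixed because it touches the primary endpoint and the remedy is cheap.

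**What to change.** In SAP 6.3, define positive as fixation on any modality performed: scintigraphy grade 1 or more, or SPECT showing fixation, or SPECT grade 1 or more if the CRF grades SPECT. Define negative as no fixation on every modality performed. State how the SPECT result is coded.

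Use the same flag for FAS2. Show as a separate undetermined row only those patients who are SPECT-positive with no grade of 1 or more on any modality, kept apart from the grade 1 patients whom the SAP already calls undetermined. If SPECT is graded, a SPECT-only patient with grade 1 or more goes under that grade, not in this row. Leave FAS3 and ATTR typing on grade 2–3.

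Keep the before/after split. Add the primary prevalence with its 95% CI under both definitions (scintigraphy grade alone; grade or SPECT) in the same patients, with counts of discordant and SPECT-only patients.

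If a grade-only endpoint was intended, it narrows the protocol's objective and should be stated as such; protocol 9.7 says that major changes to primary endpoint definitions would be reflected in an amendment.

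The cost is a few lines of derivation and one table, from variables already listed in protocol 9.3. SPECT results may be missing for patients enrolled before Amendment 2, so the table should show how many patients have one.
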